6.5. Windowing Conventions

No visit windowing will be performed for this study.

Refer to Appendix 1 for the visit convention for this study.

6.6. Statistical Tests

There will be no statistical testing performed.

6.7. Common Calculations

For quantitative measurements, change from baseline will be calculated as:

Test Value at Visit X – Baseline Value

6.8. Software Version

All analyses will be conducted using SAS version 9.4 or higher.

7. Statistical Considerations

As summaries are going to be descriptive in nature, there will not be any adjustments for covariates.

7.1. Multicenter Studies

This study will be conducted by multiple investigators at multiple centers with sites in the United States and Canada. There will be no summaries of data by site/pooled site or country.

7.2. Handling of Dropouts or Missing data

Subjects who dropped out before study completion are not to be replaced and all available information obtained from them will be included in the appropriate efficacy and safety summaries to the time of dropout. No imputation is planned for any safety measures.

If the date of the seizure is missing or incomplete and the seizure cannot be allocated to a study interval, these data will not be used in the analysis, but will be presented in the subject data listings. If the seizure diary was returned and there was no seizure data available for a day during that evaluation period, it will be assumed that the patient had missing seizure data, and the day will be excluded from the calculation of the standardized seizure frequency.

Seizure related variables will be calculated based on available data. For dropout subjects, their seizure frequency will be derived for each interval up to the last interval where the subject had data. The last interval standardized seizure frequency (SSF) will be computed based on available data prior to dropout.

7.3. Multiple Comparisons/Multiplicity

There will be no multiple comparison/multiplicity for this study.

7.4. Examination of Subgroups

Subgroup analyses will be conducted as stated in the respective primary, efficacy and safety analysis sections. The following subgroups will be assessed. Determinations of the subgroups will be based on baseline data.

Gender:

- Female
- Male

Age Groups (years):

- ≥ 18 to ≤ 65

- o > 65

Race Groups:

- o White
- o Black or African American
- o Asian
- o Other (American Indian/Alaska Native, Native Hawaiian or Other Pacific Islander, Multiple, Other)

Baseline AEDs:

- For Arm 1:
 - o Use of lamotrigine as baseline AED (yes/no)
 - o Use of levetiracetam as baseline AED (yes/no)
- For Arm 2:
 - o Use of lamotrigine as baseline AED (yes/no)
 - o Use of levetiracetam as baseline AED (yes/no)
 - o Use of carbamazepine as baseline AED (yes/no)
 - o Use of valproic acid as baseline AED (yes/no)
 - o Use of any other additional baseline AEDs that occur in $\geq 15\%$ of the subjects (yes/no)

Number of Baseline AEDs:

- For Arm 2:
 - o 1
 - o 2

Seizure Type:

- o Simple Partial
- o Complex Partial
- o Partial Evolving to Secondarily Generalized Seizures

- o Other

8. Output Presentations

Appendix 1 shows conventions for presentation of data in outputs.

The templates provided with this SAP describe the presentations for this study and therefore the format and content of the summary tables, figures and listings to be provided by IQVIA Biostatistics.

9. Disposition and Withdrawals

All subjects who provide informed consent will be accounted for in this study.

Subject disposition will be summarized and presented for the number and percentage of subjects, who were screened, screen-failed, entered, completed the study, and discontinued early including reasons for discontinuations such as adverse event, lack of efficacy, withdrawal by subject, withdrawal by investigator, protocol deviation, study terminated by Sponsor, death, pregnancy and Other.

Listing of subject disposition will also be provided.

10. Important protocol deviations

Prior to database lock, important protocol deviations (IPDs) will be identified in a review of all protocol deviations reported. Possible IPDs will include, but may not be limited to, subjects who:

- Did not meet inclusion/exclusion criteria or eligibility was not adequately verified
- Received any disallowed concomitant medication
- Developed withdrawal criteria but were not withdrawn

Individual IPDs will be presented in a data listing. The number and percentage of subjects with IPDs will be summarized by type of deviation as categorized above.

11. Demographic and other Baseline Characteristics

Demographics, including (age, gender, race, and ethnicity where applicable), and other baseline characteristics collected at screening, such as height, weight, body mass index, and disease conditions will be summarized using descriptive statistics. These data will be presented as a listing. Demographic data and other baseline characteristics will be presented for the safety and PP population.

11.1. Derivations

BMI (kg/ m²) = weight (kg)/ height (m)²

Duration of epilepsy (years) = (Date of first dose - date of epilepsy onset)/365.25

- Date of epilepsy onset: If the date of onset of epilepsy is partial, i.e. month and year recorded, or only year recorded, the missing component will be imputed with the last day of the month (where only day is missing) or 31 December (where the day and month are missing). If the date of onset is missing, the duration will not be calculated.

Age (years) = (date of informed consent – date of birth)/365.25

Baseline AEDs:

- An AED is considered to be used at baseline if it started at any time prior to the first dose of study treatment and continued. Subjects may appear in multiple AED use.

12. Medical and Epilepsy History

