8. SELECTION OF SUBJECTS

8.1. Subject Inclusion Criteria

The subjects who fulfill the following criteria will be included in the study.

1. Male or female subjects \geq 18 years of age.
2. Subject is willing and able to sign informed consent.
3. Subject has a documented diagnosis of epilepsy with simple POS with a motor component or complex POS with or without secondarily generalized seizures as defined in the Classification of Seizures of the International League Against Epilepsy (ILAE, 1981).
4. Subject has a documented electroencephalogram within 10 years prior to screening.
5. Subject has had at least 3 POS during previous six months.
6. Subject has had a sufficient number of seizures at time of enrollment to justify adjunctive therapy, as determined by the Investigator.
7. Subjects are required to be ESL-naïve AND
 - a. Maintained on a stable LEV or LTG regimen for at least 1 month (28 days) prior to screening with no history of adjunctive treatment (for Arm 1, ESL as first add-on).

OR
 - b. Maintained on a stable dose of 1-2 AEDs (excluding OXC) for at least 1 month (28 days) prior to screening and who have had prior adjunctive treatment (for Arm 2, ESL as later add-on).
8. If the subject is treated with any stimulation device for epilepsy (Vagal Nerve Stimulation [VNS], Responsive Neurostimulator [RNS], or similar), the device must have been implanted at least 6 months before screening and the device parameters must be documented as stable for at least 1 month prior to screening. (Note: these devices will not be counted as concomitant AED).
9. Except for epilepsy, subject is judged to be in general good health based on medical history, physical examination findings, and clinical laboratory test results.

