3.1. General Description

This is a 31-week, multicenter, 2-arm, prospective, open-label, non-randomized, Phase 4 study of ESL as adjunctive therapy in adult subjects with a diagnosis of epilepsy with POS. Two groups of ESL-naïve subjects will be evaluated. The groups are defined as follows:

Arm 1 (ESL as first add-on): This group will include subjects who have been maintained on a regimen consisting of a stable dose of LEV or LTG for at least 1 month (28 days) prior to screening and who have not used any adjunctive treatment.

Arm 2 (ESL as later add-on): This group will include subjects who have been maintained on a regimen consisting of a stable dose of 1 - 2 anti-epileptic drugs (AEDs) (excluding oxcarbazepine [OXC]) for at least 1 month (28 days) prior to screening and who have used adjunctive treatment in the past.

The Arm 1 subjects will allow an assessment of the efficacy and safety of ESL in subjects who are early in the course of their disease and being treated with one of the most common first line AEDs. The subjects in Arm 2 are similar to the subject population in the Phase 3 adjunctive studies, treatment-resistant subjects who are later in the course of their disease. The inclusion of these subjects in the present study will provide an assessment of the efficacy and safety of ESL as a later adjunctive therapy in a real world clinical setting. In addition, this study will provide data from both Arm 1 and Arm 2 for several behavioral, mood-related, and QOL-related assessments that were not evaluated in the Phase 3 program.

Approximately 100 subjects will be enrolled (approximately 50 subjects in Arm 1 and 50 subjects in Arm 2).

The study will consist of a Screening Phase of 1 to 2 weeks, followed by a 2-week Titration Phase, a 24-week Maintenance Phase, and a Safety Follow-up/Taper Phase of 4 weeks. The last visit in the Maintenance Phase (Visit 9) is considered the End of Study (EOS) visit.

The screening visit should take place 7 - 10 days prior to the titration visit and may be extended to 7 - 17 days if required with consent of medical monitor. Subjects of Asian ancestry who require HLA-B*1502 testing (eg do not have prior test results) may have the screening visit 7 - 17 days prior to the titration visit.

Subjects who withdraw prior to the EOS visit should have an Early Discontinuation Visit (EDV) within 72 hours.

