12.2. Epilepsy History

Epilepsy information will be collected and summarized descriptively for the safety population.

Epilepsy summary will include age at onset of epilepsy in years and years since onset of epilepsy (refer to section 11.1 for derivation). Category of possible etiology for epilepsy will also be summarized.

Listing of epilepsy history will be provided.

13. Prior and Concomitant Medications

Medications will be presented for the safety population and coded using WHO Drug version 01MAR 2017.

The number and percentage of subjects using each concomitant medication will be summarized overall according to the WHODRUG Anatomic Therapeutic Class (ATC) Level III and preferred term for concomitant AED and non-AED medication separately. Subjects with multiple uses of a concomitant medication will be counted once by the ATC level and preferred term.

See Appendix 2 for handling of partial dates for medications, in the case where it is not possible to define a medication as prior, concomitant, the medication will be classified by the worst case; i.e. concomitant.

- Prior medications are medications which started and stopped prior to the first dose of study medication.
- Concomitant medications are medications which started at the same time of or after the first dose of study medication and at the same time of or before the last dose of study medication; or started prior to and ended at the same time of or after the first dose of study medication; or started at the same time of or prior to the last dose of study medication and marked as ongoing.
- Post-treatment medications are medications which started after the last dose of study medication.

Listings of concomitant AED, non-AED medications, prior, and post-treatment medications will be provided.

14. Study Medication Exposure

The extent of exposure will be summarized descriptively: it will be calculated as the date of last dose minus the first dispensed dose date, ignoring missing days plus 1. If subject last dose is missing, subject last contact date will be used.

The date of first study medication and the date of the last dose will be taken from the Study Drug Dispensation and Disposition source, respectively.

Duration of exposure, the date of first dose, date of last dose, date of the change dose, amount, and reason for dose change will be listed.

Frequency of duration of exposure will be summarized using the following categories:

1 day - < 3 weeks

=> 3 - < 7 weeks

=> 7 - < 9 weeks

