	Partial	Impute stop date as latest possible date: 
 • If only day unknown, impute as the earlier of (last day of month, end date of the last study visit) • If month and day unknown, impute as the earlier of (31st December, end date of the last study visit). Then: If stop date < study med start date, assign as prior If stop date >= study med start date and start date <= end of treatment, assign as concomitant If stop date >= study med start date and start date > end of treatment, assign as post treatment
	Missing	If stop date is missing could never be assumed a prior medication If start date <= end of treatment, assign as concomitant If start date > end of treatment, assign as post treatment

START DATE	STOP DATE	ACTION
Partial	Known	
Impute start date as earliest possible date: Source questions: 'started prior to start of study?' = Yes; 'Started after last dose of study medication?' = No.
 
 • If only day unknown, impute as the later of (first day of the month). • If month and day unknown, impute as the later of (1st January). 
Source questions: 'Started prior to study?' = No; 'Started after last dose of study medication?' = Yes.
 
 • If only day unknown, impute as the later of (first day of the month; end of treatment + 1). • If month and day unknown, impute as the later of (1st January; end of treatment + 1). 
Source questions: 'Started prior to study?' = No; 'Started after last dose of study medication?' = No.
 
 • If only day unknown, impute as the later of (first day of the month; date of ICF). • If month and day unknown, impute as the later of (1st January; date of ICF). 
Then:
 
If stop date < study med start date, assign as prior.
 
If stop date \geq study med start date and start date \leq end of treatment, assign as concomitant.
 
If stop date \geq study med start date and start date $>$ end of treatment, assign as post treatment.

		
treatment, assign as concomitant.
 
If stop date \geq study med start date and start date $>$ end of treatment, assign as post treatment.

	Partial	

START DATE	STOP DATE	ACTION

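### A partial epilepsy onset date is imputed to the latest possible day with no upper bound, so duration is never overstated and is negative when a year-only onset falls in the year of first dose

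*SAP*

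**What the plan says.** SAP section 11.1 defines the variable as "Duration of epilepsy (years) = (Date of first dose - date of epilepsy onset)/365.25". A partial onset date is "imputed with the last day of the month (where only day is missing) or 31 December (where the day and month are missing". For a wholly missing date, "If the date of onset is missing, the duration will not be calculated". The section gives no cap at first dose, consent or screening, no floor at zero, and no separate rule for an onset in the same period as first dose.

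The derived value is used for the safety population in SAP section 12.2, which reads: "Epilepsy summary will include age at onset of epilepsy in years and years since onset of epilepsy (refer to section 11.1 for derivation"). Section 11.1 has a formula for duration but none for age at onset.

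Appendix 2 holds the SAP's other partial-date rules. It covers adverse events and medications only. For medication stop dates it does bound a latest-date imputation: "If only day unknown, impute as the earlier of (last day of month, end date of the last study visit"). It has no counterpart for epilepsy onset.

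**The concern.** Imputing onset to the end of the known period gives an error in one direction, so averaging over subjects does not remove it. Without a bound, the imputed onset can also fall after the first dose. That produces a negative duration, which is impossible for a subject enrolled because of existing epilepsy.

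At stake is the credibility of one baseline table. The SAP describes Arm 1 as "subjects who are early in the course of their disease and being treated with one of the most common first line AEDs", so recent onset, and with it a year-only onset in the first-dose year, is most plausible there. A negative minimum in that table would prompt queries. Appendix 2 keeps imputed dates out of the listings, so the listing would show the recorded partial date but not the date that produced the value.

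**Working it through.** The plan states no figure for this derivation, so there is none to reproduce. The check is date arithmetic on the rule as written.

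**Inputs**
- Duration formula and imputation rule: SAP section 11.1.
- Minimum time on stable treatment: 28 days before screening. For Arm 1, Protocol section 8.1 has "Maintained on a stable LEV or LTG regimen for at least 1 month (28 days) prior to screening"; Arm 2 has the same minimum.
- Minimum gap from screening to first dose: 7 days (SAP section 3.1).
- Assumption: true onset is uniform over the days of the known year or month. The documents give no distribution.

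**Size of the understatement** (imputed date minus true date)
- Year only, 365-day year: errors run from 0 to 364 days. Mean = (0 + 1 + ... + 364)/365 = 182 days; 182/365.25 = 0.50 year. Maximum = 364/365.25 = 1.00 year. In a leap year the mean is 182.5 days and the maximum 365 days.
- Day missing, 365-day year: a month of n days contributes n(n-1)/2. Seven months of 31 days give 7 x 465 = 3255, four of 30 days give 4 x 435 = 1740, and February gives 378. Mean = 5373/365 = 14.7 days = 0.04 year. Maximum = 30/365.25 = 0.08 year.
- The error is zero if true onset was the last day of the period, and it never has the opposite sign.

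**Year-only onset in the calendar year of first dose** (example year 2018)

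| First dose | Days from first dose to 31 Dec | SAP duration (years) |
|---|---|---|
| 1 Mar | 305 | -0.835 |
| 15 Jun | 199 | -0.545 |
| 15 Oct | 77 | -0.211 |
| 30 Dec | 1 | -0.003 |
| 31 Dec | 0 | 0.000 |

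**Can this happen in an eligible subject?** If the AED was started for the epilepsy, onset is at least 28 + 7 = 35 days before first dose. Onset in the same calendar year is then possible for any first dose from 5 February onward, which is 365 - 35 = 330 of 365 days. For a first dose on 15 June 2018 the true duration would lie between 35 days (0.096 year) and 165 days (0.452 year), while the rule returns -0.545.

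**How often, among year-only dates with recent onset?** Suppose onset is uniform over 35 to 365 days before first dose and first-dose dates are uniform over the year. For a gap of g days, the chance of sharing the calendar year is 1 - g/365. The mean gap is (35 + 365)/2 = 200 days, so the share is 1 - 200/365 = 45%.

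**Day-missing onset in the month of first dose.** The rule would give, for example, -17/365.25 = -0.047 year for a first dose on 14 October. But 35 days is longer than any month, so an eligible subject cannot have this pattern. If onset is in an earlier month than first dose, the month-end imputation stays before first dose and the duration is positive.

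**The case against.** The strongest reply is that this is one prespecified, reproducible convention for one descriptive variable. The SAP plans no between-arm comparison and no statistical testing (sections 6.1 and 6.6). Duration is not a subgroup factor in section 7.4 and enters neither the retention endpoint nor any seizure endpoint. Continuous summaries include the median and quartiles, which a few odd values barely move, and the minimum would expose a negative value. The day-missing error is negligible. All of this stands and is why the point is minor. It does not answer the impossible values, because a prespecified rule that can date onset after treatment is still wrong as written.

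A reader might infer more than the documents support:
- *That every partly dated duration is understated.* The error is zero when true onset was the last day of the period, so the accurate statement is that duration is never overstated.
- *That same-month onset also gives negative values.* The rule allows it, but the 35-day minimum excludes it for eligible subjects. It would take an eligibility violation, or an AED not started for the epilepsy.
- *That the rule undermines the early-versus-late distinction between the arms.* The arms are defined by prior AED treatment (Protocol sections 7.2 and 8.1; SAP section 3.1), not by duration, and no passage makes the duration summary the test of that distinction.
- *That age at onset is raised.* Section 11.1 has no formula for it, and it may be collected directly. It is affected only if it is derived from the imputed date.

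It can also be said that midpoint rather than period-end is a preference. In part it is. The missing upper bound is not, and a midpoint alone would not supply one.

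**Conclusion.** The point holds at minor severity. Followed exactly, SAP section 11.1 gives partly dated durations that are never overstated, with a mean understatement of about 0.50 year (up to 1.0) for year-only dates and 0.04 year (up to 0.08) where only the day is missing. It gives a negative duration whenever only the year is known and it is the year of first dose, or exactly zero if first dose is on 31 December.

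The averages assume uniform true dates. The 45% share applies only to year-only cases with onset 35 to 365 days before first dose. The documents do not say how many onset dates are partial, so the effect on the reported mean cannot be calculated and could be nil. The damage is limited to the years-since-onset summary in SAP section 12.2, plus age at onset if it is computed from the same date.

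**What to change.** Replace the imputation sentence in SAP section 11.1 with a bounded midpoint rule:
- use day 15 when only the day is missing, and 1 July when day and month are missing;
- cap the imputed date so that it cannot fall after informed consent, or after an earlier date known to follow onset, such as the recorded start of the first AED for epilepsy;
- state whether age at onset is collected or derived and, if derived, use the same imputed date.

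Midpoint imputation brings the mean error to about zero, with a range of about ±0.50 year (year only) or ±0.04 year (day missing). The cap is still needed: with 1 July 2018 imputed and first dose on 15 June 2018, the midpoint alone gives -16/365.25 = -0.04 year. Consent is taken at screening, at least 7 days before first dose, so the consent cap guarantees a positive value. It still allows an onset later than 28 days of prior treatment would permit, so the AED start date is the better bound where it is recorded.

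The cost is one SAP sentence and about one line of code, with no new data and no effect on any other analysis.

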12.1. Medical History

Medical history will be coded using (MedDRA), version 13.1, and presented for the safety population by SOC and PT.

A data listing of medical history will be provided.

12.2. Epilepsy History

Epilepsy information will be collected and summarized descriptively for the safety population.

Epilepsy summary will include age at onset of epilepsy in years and years since onset of epilepsy (refer to section 11.1 for derivation). Category of possible etiology for epilepsy will also be summarized.

Listing of epilepsy history will be provided.

13. Prior and Concomitant Medications

Medications will be presented for the safety population and coded using WHO Drug version 01MAR 2017.

The number and percentage of subjects using each concomitant medication will be summarized overall according to the WHODRUG Anatomic Therapeutic Class (ATC) Level III and preferred term for concomitant AED and non-AED medication separately. Subjects with multiple uses of a concomitant medication will be counted once by the ATC level and preferred term.

See Appendix 2 for handling of partial dates for medications, in the case where it is not possible to define a medication as prior, concomitant, the medication will be classified by the worst case; i.e. concomitant.

- Prior medications are medications which started and stopped prior to the first dose of study medication.
- Concomitant medications are medications which started at the same time of or after the first dose of study medication and at the same time of or before the last dose of study medication; or started prior to and ended at the same time of or after the first dose of study medication; or started at the same time of or prior to the last dose of study medication and marked as ongoing.
- Post-treatment medications are medications which started after the last dose of study medication.

Listings of concomitant AED, non-AED medications, prior, and post-treatment medications will be provided.

14. Study Medication Exposure

The extent of exposure will be summarized descriptively: it will be calculated as the date of last dose minus the first dispensed dose date, ignoring missing days plus 1. If subject last dose is missing, subject last contact date will be used.

The date of first study medication and the date of the last dose will be taken from the Study Drug Dispensation and Disposition source, respectively.

Duration of exposure, the date of first dose, date of last dose, date of the change dose, amount, and reason for dose change will be listed.

Frequency of duration of exposure will be summarized using the following categories:

1 day - < 3 weeks

=> 3 - < 7 weeks

=> 7 - < 9 weeks

=> 9- < 11 weeks
=> 11- < 15 weeks
=> 15- < 17 weeks
=> 17- < 19 weeks
=> 19- < 23 weeks
=> 23- < 27 weeks
>= 27 – <= 31 weeks
> 31 weeks

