9.4. Study Drug Accountability

The Investigator or designee will maintain accountability records, including the availability of study drug received, study drug dispensation and returns per Sponsor/contract research organization (CRO) instructions.

The date of the first dose of study drug and the amount, the date of last dose of study drug and the amount, and the date of any change of study drug dose and the amount with the reason for the dose change for each alteration will be collected in the database.

The Investigator or designee will collect and document the status of all used and unused study drug from study subjects at appropriate study visits per Sponsor/CRO instructions.

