10.1.2. Premature Discontinuation of Treatment with Study Drug

Subjects who prematurely discontinue treatment with ESL prior to Visit 9 (EOS) for any reason will be gradually tapered off study drug (see Table 5). However, abrupt discontinuation of the drug is permitted for the treatment of an AE. Subjects who prematurely discontinue treatment with ESL (abruptly, or by taper) will be withdrawn from the study.

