11.5.11. Early Discontinuation Visit

Subjects who withdraw prior to the EOS visit should have an early discontinuation visit (EDV) within 72 hours. Every effort should be made for all subjects prematurely discontinuing the study drug, regardless of cause, to undergo final evaluation described below:

- Record concomitant medications.
- Perform physical and neurological examination.
- Obtain vital signs and body weight.
- Perform a 12-lead ECG.
- For females of childbearing potential, obtain blood for serum β -hCG.
- Obtain blood and urine sample for clinical laboratory testing (including thyroid panel).
- Record LAEP.
- Record AEs.
- Collect study drug.
- Record any AED dose change since the last study visit.
- Collect paper seizure diary
- Distribute paper seizure diary
- Review seizure diaries.
- Administer questionnaires (EQ-5D, CGI-I, PGI-C, QOLIE-31, POMS-SF, NDDI-E, MOAS, and eC-SSRS).
- Dispense study drug if needed for taper.
- Ensure return of watch and data collection device.

11.5.12. Follow-up Visit: Visit 10 or Telephone Call 3 (Week 31 ± 7 days)

- Record AEs.
- Record concomitant medications.
- Review paper seizure diary.

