14.1. Derivations

Duration of exposure (days) = date of last study medication – date of first study medication + 1.

15. Outcomes Variables

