15.2.1.5. Time on ESL

Time on ESL will be calculated from the first dose as indicated in the Study Drug Dispensation source to the last known dose of ESL in the Disposition source. Subjects who were still on ESL at the end of study will be censored at the end of study. Subjects who dropped out of the study

while receiving treatment will be an event at the time of the last dose date. Change in dosage levels during the treatment period will be ignored.

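### SAP section 14 replaces a missing last-dose date with an undefined, uncapped last contact date, so time after study ESL has stopped can be counted as exposure

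*SAP*

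**What the plan says.** SAP 14.1 defines "Duration of exposure (days) = date of last study medication – date of first study medication + 1". Section 14 takes the last-dose date from the Disposition source and adds the fallback "If subject last dose is missing, subject last contact date will be used". The result is summarized descriptively and tabulated in eleven duration bands, several of them only two weeks wide.

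Time on ESL (SAP 15.2.1.5) runs "to the last known dose of ESL in the Disposition source". It gives no instruction for a blank date.

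Protocol 9.4 lists the items to be held in the database, beginning "The date of the first dose of study drug and the amount, the date of last dose of study drug and the amount". The fallback is therefore meant for exceptions.

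The last scheduled contact is given in protocol 11.5.12: "Follow-up Visit: Visit 10 or Telephone Call 3 (Week 31 ± 7 days". SAP 3.1 describes "a 24-week Maintenance Phase, and a Safety Follow-up/Taper Phase of 4 weeks". For early leavers, protocol 10.1.2 says "Subjects who prematurely discontinue treatment with ESL (abruptly, or by taper) will be withdrawn from the study", and 11.5.11 says "Subjects who withdraw prior to the EOS visit should have an early discontinuation visit (EDV) within 72 hours". Taper drug can be dispensed at the EDV and at Visit 9 (protocol Table 2, notes k and p). The Table 5 tapers involve one or two weeks of dosing. Completers may instead move to commercial ESL.

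SAP 3.4.2 drops number of doses and average daily dose because accountability data were not collected.

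**The concern.** The follow-up contact exists to observe subjects after study treatment. Using its date as a last-dose date counts time off study drug as time on it. Whenever that contact is the one used, the error goes in one direction: exposure is lengthened, and subjects can move up the duration bands. With doses taken and average daily dose no longer reported, duration is the main exposure summary left. Nothing in the SAP would show a reader how many durations end on an imputed date. Because Time on ESL has no matching rule, the same blank date could also be handled differently in two outputs of one report.

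**Working it through.** **The plan's own figure.** Titration 2 + maintenance 24 + follow-up/taper 4 = 30 weeks, which matches the treatment duration in the protocol synopsis.

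**Day numbers.** Week w starts on Day 7(w − 1) + 1. This gives Day 15 for Week 3, Day 29 for Week 5, Day 57 for Week 9, Day 183 for Week 27 and Day 211 for Week 31. With Day 1 as first dose, exposure equals the day number of the end date. An end date at Week 31 gives 211 days = 30.1 weeks; ±7 days gives 204 to 218 days (29.1 to 31.1 weeks).

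**Early leaver with a blank last-dose date.** The overstatement depends on which contact was last, taking the last dose as the day of withdrawal with no taper:

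| Last contact | Overstatement |
|---|---|
| EDV within 72 hours | at most 3 days |
| 4 weeks after the EDV (assumption) | 3 + 28 = 31 days; 31 + 7 = 38 with the window |
| Calendar Week 31, stop on Day 29 | 211 − 29 = 182 days (26 weeks) |
| Calendar Week 31, stop on Day 57 | 211 − 57 = 154 days (22 weeks) |

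Taper dosing shortens these gaps. In the second row, one or two weeks of taper leaves 31 − 7 = 24 or 31 − 14 = 17 days. If the EDV is the last contact and taper drug is taken afterwards, the substituted date can be slightly too early.

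**Effect on the bands.** A stop on Day 15 is 2.1 weeks, in the band below 3 weeks. An EDV date gives 18 days (2.6 weeks), the same band. EDV + 4 weeks gives 46 days (6.6 weeks), in the 3 to <7 band; a further 7 days gives 53 days (7.6 weeks), in 7 to <9. Calendar Week 31 gives the 27 to 31 band.

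**Completer with a blank last-dose date.**
- No taper: 211 − 183 = 28 days. The band moves from 23 to <27 (26.1 weeks) to 27 to 31 (30.1 weeks). For someone who went on to commercial ESL this is time off study drug, though not off ESL.
- One week of taper: last dose about Day 190, so 211 − 190 = 21 days.
- Two weeks of taper: about Day 197, so 211 − 197 = 14 days. Both tapered cases (27.1 and 28.1 weeks) are already in the 27 to 31 band, so the nominal band does not change.

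**Arm mean.** With 50 subjects per arm (SAP 3.1) and k affected, the shift is k × overstatement / 50.

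| k | 31 days each | 154 days each |
|---|---|---|
| 1 | 0.6 days | 3 days |
| 3 | 1.9 days | 9 days |
| 5 | 3.1 days | 15 days |

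The values of k are illustrative, because the documents do not give the number of missing dates. The 154-day column requires the calendar Week 31 reading and a Day 57 stop.

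**The case against.** The strongest reply is that the trigger is narrow. The last-dose date is a planned data item, so the rule acts only when it is blank. Harm also needs a contact well after treatment, and a subject reached at follow-up can simply be asked when dosing stopped. Subjects with a blank date may more often be those lost to follow-up, whose last contact could well be on treatment. All of this stands. It limits how often the error occurs, but it does not make the rule right when it is applied.

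A reader might infer that an early leaver will be tabulated with about 30 weeks of exposure. The documents do not support that as a general statement. Early leavers are withdrawn, should be seen within 72 hours, and enter a follow-up phase described as lasting 4 weeks. The schedule prints only Week 31 for the follow-up contact and does not re-time it for them, but nothing says they are followed to that date either. The 26-week figure is therefore an upper bound on one reading.

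A reader might also infer that the retention result or the adverse event rates are distorted. Retention is completion of Visit 9 over the safety population (SAP 15.1.1) and uses no exposure date. Adverse events are reported as subject incidence and event counts (SAP 16.1), with no exposure-adjusted rate specified.

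**Conclusion.** The point holds as a defect in one derivation. The fallback is undefined and uncapped, and when it picks up the safety follow-up it overstates study-drug exposure. The likely size per affected early leaver runs from a few days to about a month. The month rests on the assumption that follow-up comes 4 weeks after the EDV. Anything near 26 weeks rests on contact at calendar Week 31, which is unconfirmed. For completers it is 28 days without taper and about 14 to 21 with taper, before visit windows. The effect on an arm mean is small unless several dates are missing or the calendar reading applies. The damage is confined to the descriptive exposure summary.

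The difference from Time on ESL is a gap, not a demonstrated contradiction: both use the Disposition source, and only one says what to do with a blank. Starting exposure from the dispensing record might also look like an error, but drug is dispensed at Visit 2, which is Day 1, and Time on ESL starts from the same source. Nor would a subject who never took ESL enter the summary, because the safety population requires at least one dose.

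**What to change.** Before database lock, replace the sentence in SAP section 14 with: *If the last-dose date is missing, use the latest date on which the records show study ESL was being taken (dose-change record, on-treatment visit or call, or recorded taper dosing); a post-treatment follow-up contact alone is never used.* Apply the same date to Time on ESL in 15.2.1.5, and footnote the exposure table with the number of subjects whose end date was imputed.

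A hard stop at the EDV or Visit 9 would be the wrong repair: taper drug is dispensed at those visits, so it would delete real exposure.

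The cost is one sentence and one derivation. The downside is that exposure may be slightly understated where taper dosing was not recorded, or for subjects lost to follow-up who kept taking drug after their last record.
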